benefit obtained when both are used together.^{50,52-53} The combination of exercise and plasticity-based CT has not been previously tested in HF or in other populations as an intervention for improving cognitive outcomes,^{50,64-66} but may be most optimal for targeting the underlying mechanisms for CI in HF. The proposed feasibility study is designed to test the acceptability, implementation and limited efficacy of a combined exercise (Ex) and cognitive training (CT) intervention in stable NYHA class II and III heart failure patients with cognitive impairment. A total of 60 participants will be randomized to one of three study arms: Ex/CT (N=20), Ex-alone (N=20), and attention control (N=20). The study aims are:

Aim 1: To evaluate the feasibility of a 3-arm intervention (ExCT, Ex, AC) in heart failure patients with CI.

Aim 1a. To test the acceptability and implementation of each study arm.

Aim 2: To ascertain limited efficacy of the 3-arm intervention on changes in cognitive abilities

Aim 3: To ascertain limited efficacy of the 3-arm intervention to improve cerebral oxygenation, physiological status, physical function and QOL.

A. Significance. Approximately 670,000 individuals are diagnosed with HF annually in the United States,⁶⁷⁻⁷⁰ and over one million hospitalizations occur each year due to HF, especially among adults 65 years of age and older.⁷¹⁻⁷³ As many as 60% of persons with HF experience cognitive impairment, (CI); this number increases proportionately as HF worsens.^{5-6,10,74-76} Increased age and depression are independent predictors of more severe CI in persons with HF.^{5-6,77-82} CI often interferes with the ability to engage in effective self-management of HF; this leads to more frequent hospitalizations and contributes to the cost burden on the health care system and reduced quality of life.^{6,74-75,83} To reduce these burdens, we propose a nurse-led exercise and cognitive training intervention that targets underlying mechanisms that contribute to CI in persons with HF.

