Cognitive training. The type of CT that produces the best cognitive function outcomes is unknown since many studies have enrolled predominately healthy, well-educated white individuals with no CI.⁶⁴⁻⁶⁶ Research in adults with CI are inconclusive and have considerable limitations; few randomized trials are available.^{64-66,88} Several recent studies suggest that computer-based plasticity interventions may be advantageous, e.g. in memory training.⁸⁹⁻⁹¹ Plasticity-based training interventions hinge on the understanding that targeted, repeated cognitive exercises can rebuild and re-organize function through neuronal generation, dendritic sprouting, and axonal sprouting. The only study to date to incorporate plasticity-based cognitive training in HF found that it significantly increased list learning, delayed recall memory, psychomotor speed, and performance of IADLs; participant adherence and satisfaction were high.¹⁶ In another study of community dwelling older adults without CI, improvement in memory and attention was significantly greater in the group that received the plasticity-based cognitive training intervention than in those receiving a program of general cognitive stimulation.

Combined exercise and CT. Evidence of exercise improving cognitive function is **robust**; and similar changes on cognition are noted with plasticity-based CT; the effects of these two approaches are different yet synergistic, and suggest the effect on cognitive functioning may be more pronounced when the two are used in combination versus alone; this provides a strong rationale for the proposed intervention.⁵²⁻⁶⁶ This feasibility study will evaluate the acceptability of the intervention(s), adherence to the intervention protocols, the scope of

recruitment efforts to identify acceptable cases, potential dose responses gleaned from differing amounts of intervention compliance, and estimates of effect sizes to optimize a subsequent, large-scale efficacy trial.

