Since the intent of this study is exploratory; hypothesis testing will not be the primary focus of the statistical analysis. Rather, we will analyze data with the specific intent of establishing population parameters (e.g., effects sizes) for the variables being investigated. Confidence intervals will be calculated for all effect sizes associated with the predictor variables, other significant outcome effects, and for changes over time. These effect size estimates will be used to design the future R01 study. Given the relatively small sample size of $n=60$ at 80% power, and $\alpha=.05$, we will have the ability to detect a moderate ($d=.5$) to large effect size ($d=.8$). We will use

general linear and/or mixed models as the main modeling framework for analyses of the outcome measures in the projects. We will build full factorial models to test for interactions and review estimated marginal means. We will use Using G*Power 3, to estimate actual power for the GLM analysis both a priori and post hoc.

E. HUMAN SUBJECTS RESEARCH

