Rationale for sample characteristics. The age range was selected to avoid confounding effects of age and sarcopenia with outcomes such as aerobic capacity, BDNF and HRQOL; participants below the age of 40 years are likely to have HF for other reasons than the majority of the general HF population. Older age (>75) is associated with reduced exercise capacity and age related cognitive decline which may confound physical function cognitive outcome measurement. In addition, persons over the age of 75 are at higher risk for adverse events during exercise testing and with aerobic exercise. Although we anticipate most participants to be receiving optimal medication therapy, treatment decisions regarding individual care will be based on patient's clinician; evidence-based care will be encouraged. If any participants are not being treated with what is considered optimal medication therapy according to ACC guidelines, the reason (eg, intolerance) will be recorded and tracked by group and statistically controlled as a covariate. We recognize that both resting and exercise heart rates are influenced by beta-blockers, which is considered optimal therapy for HF patients. For both exercise testing and training we will use the heart rate reserve method which takes into account the patient's resting heart rate, thereby reducing the effect of beta-blockade. We will attempt to schedule patients for their exercise testing and training a minimum of 3 hours after taking beta blockers.²⁸⁻²⁹ For patients who are unable to schedule exercise during this time frame or exercise up to the prescribed heart rate, Borg's 6-20 rate of perceived exertion scale (RPE) between 12-15, will be used to guide exercise intensity, consistent with a moderate intensity level exercise. Patients with an ICD may be enrolled if their heart rate limits are set to be higher than the target heart rate for the exercise regimen. In our last preliminary study, approximately 90% had an ICD; there were no firings during exercise or any increase in adverse events. Although unlikely to occur, participants with a fixed rate pacemaker would not be able to participate because heart rate may be set at a lower rate than required to achieve prescribed target heart rate. Participants who have recurrent angina, more severe symptoms have uncontrolled hypertension will be excluded due to the higher risk for adverse cardiovascular events during exercise testing and the walking intervention. Because moderate to severe depressive symptoms are a major predictor of exercise attrition and more severe CI, participants will be excluded who have a BDI-II score of 25 or higher. These severely depressed subjects will be evaluated for suicidal risk, and referred to psychiatric care. Because the benefit of exercise is being evaluated, participants who are currently enrolled, or were recently enrolled in an exercise program for the past 8 weeks, currently exercising at regular intervals (more than twice per week for 30 minutes) will not be eligible for the study.

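### Dose response is to be read from how much participants complied, which is not randomised and is likely to follow health, so a programme with no effect could still show a gradient

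*Combined protocol and SAP*

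**What the plan says.** The paragraph on combined exercise and CT (section A, Significance) lists what the study will evaluate. The list includes "potential dose responses gleaned from differing amounts of intervention compliance, and estimates of effect sizes to optimize a subsequent, large-scale efficacy trial". Data Management and Analysis adds, of the planned effect sizes, that "These effect size estimates will be used to design the future R01 study".

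Dose is not a randomised factor. Both exercise arms follow one prescription (section C, exercise prescription table), and every ExCT participant is given the same Brain Fitness programme.

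Several statements bear on who will comply:

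- The rationale for sample characteristics (section E) opens a sentence with "Because moderate to severe depressive symptoms are a major predictor of exercise attrition and more severe CI". The same sentence goes on to exclude people with a BDI-II score of 25 or higher.
- The Significance section says "CI often interferes with the ability to engage in effective self-management of HF".
- The account of walking risks (section E) tells participants with symptoms, more breathlessness or rapid weight gain not to exercise. It also holds symptomatic participants at their current level until they tolerate it.

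On analysis, the Adherence paragraph (section C) says only that actual adherence and attrition will be included in an intent-to-treat analysis; it gives no model. Data Management and Analysis describes comparisons between arms, controlling for covariates that include depression, NYHA class, medications and comorbidities. Baseline cognition and baseline peak VO2 are not named. The exercise adherence score is the sum of weekly scores divided by the number of weeks walked.

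**The concern.** Comparing high with low compliers inside an arm is an observational comparison placed within a trial. If people who are less depressed, less impaired or clinically steadier do more sessions and also do better on the tests, the comparison credits the programme with a difference that they brought with them. Part of this arises after baseline: heart failure that worsens during the 12 weeks reduces walking under the protocol's own safety instructions, and may also worsen the outcome. Baseline covariates cannot fully remove that.

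What is at stake is the use made of the result. The dose-response reading is listed among the things meant to optimise the efficacy trial. A gradient produced by health would make more training look more effective than it is. A larger sample would estimate the same biased quantity more precisely.

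**Working it through.** The plan gives no dose-response model, slope or precision, so there is no figure of its own to reproduce. The size of the bias has to be worked out from assumptions, because the documents give none of the correlations needed.

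**Assumptions.** The true effect is zero. A baseline health trait has correlation *a* = 0.3 to 0.5 with compliance and *b* = 0.3 to 0.6 with the cognitive score. 70% of participants count as compliant. The test-retest correlation ρ of the score is 0.6 to 0.8.

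**1. Raw follow-up score.** The induced correlation between compliance and score is *a × b*, from 0.3 × 0.3 = 0.09 to 0.5 × 0.6 = 0.30. For a 70/30 split of a normal compliance variable, the gap in SD units is *d = ab × φ(c) / (0.7 × 0.3)*. With c = −0.524 and φ(c) = 0.3477, the multiplier is 0.3477 / 0.21 = 1.656.

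- Low end: 0.09 × 1.656 = 0.15 SD.
- High end: 0.30 × 1.656 = 0.50 SD.

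**2. Adjusted for the baseline score.** Let the trait affect baseline and follow-up equally, so that both show the gap *d*. The adjusted gap is *d(1 − ρ) / (1 − r²)*, where *r = d × √0.21* is the correlation of the compliant/non-compliant indicator with the score.

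- Low end (d = 0.149, ρ = 0.8, r = 0.068): 0.149 × 0.2 / 0.995 = 0.03 SD.
- High end (d = 0.497, ρ = 0.6, r = 0.228): 0.497 × 0.4 / 0.948 = 0.21 SD.

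**3. Change score.** Under the same equal-effect assumption the gap is d − d = 0. A spurious gradient in change requires the trait to predict change, and not only level.

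**4. If the trait does predict change.** Let *b* now be its correlation with change. The expected compliance-change correlation is again *ab*. The table gives simulated two-sided 5% tests with no true effect. The adjusted column adds a baseline covariate correlated 0.7 with the trait.

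| a, b | n = 20, mean r | n = 20, significant | n = 20, adjusted | n = 40 (exercise arms pooled), significant |
|---|---|---|---|---|
| 0.3, 0.3 | 0.09 | 6–7% | 5% | 8–9% |
| 0.5, 0.5 | 0.24 | 18–19% | 9% | 35% |
| 0.7, 0.7 | 0.48 | 61–62% | 28% | 91% |

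With a covariate that captures the trait perfectly, the rate returns to about 5%.

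**5. The exercise dose measure.** Someone who completes two full weeks and then stops has weekly scores of 100% and 100%. Divided by weeks walked, the score is 200 / 2 = 100%. Divided by the 12 weeks prescribed, it is 200 / 12 = 17%. The planned score can therefore rank an early stopper with full adherers.

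**6. A complier-average estimate based on the 80% rule.** The rule is 0.8 × 2400 = 1920 minutes. Dividing the ExCT–Ex difference by the share who reach it assumes that fewer minutes do nothing. Suppose instead that benefit is proportional to minutes, with 70% of people spread evenly over 80–100% of the programme (mean 0.9) and 30% spread evenly over 0–80% (mean 0.4). The arm difference is 0.7 × 0.9 + 0.3 × 0.4 = 0.75 of the full-programme effect. Dividing by 0.7 gives 1.07, against 0.90 among those who meet the rule: about 19% too high.

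**The case against.** The other side has substantial points.

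- **The severe end of depression is excluded.** The sentence linking depression to attrition does so to justify the BDI-II cut-off. Depression, NYHA class and comorbidities are also listed as covariates. This narrows the pathway but does not close it: milder depression remains, and baseline cognition and peak VO2 are not named.
- **The evidence on compliance is indirect.** The remark on cognitive impairment concerns self-management of heart failure, not walking or computer training. The protocol reports adherence of 80% or more in the exercise pilot and high adherence in the earlier heart failure study of the same CT program. That the healthier will comply more here is a reasonable inference, not a documented fact.
- **The plan studies change.** The largest gaps belong to an unadjusted follow-up score. More impaired participants also have more room to improve and may regress towards the mean, which could reverse the sign.
- **The clause is modest.** It speaks of potential dose responses, stands in the background section, is not among the aims, and belongs to a study that calls itself exploratory.

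These points limit the size of the problem. None of them makes compliance a randomised exposure. Low rates of false significance are only partial comfort, because the plan puts estimation ahead of testing and it is the estimate that would be carried forward.

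A reader might go further and infer that an ineffective programme *would* show a dose response. The documents do not support that: under weak confounding the false-positive rate is close to nominal.

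**Conclusion.** The concern holds in a limited form. The plan intends to learn about dose from compliance that is not randomised, its own text gives reasons for compliance to follow health, and nothing in the analysis section guards against that. A null programme could show a gradient. Under the stated assumptions the spurious gap is 0.15 to 0.50 SD in raw follow-up scores and about 0.03 to 0.21 SD after baseline adjustment. It is zero in change scores if the trait acts equally on baseline and follow-up. The direction is probably favourable, but that is not certain.

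Three stronger inferences should be resisted:

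- **That the trial's main comparison is biased.** The randomised contrasts are untouched unless adherence is put into that model. The Adherence paragraph may intend this, but it is too brief to tell.
- **That the spurious gap matches the one-third SD improvement the protocol cites for Brain Fitness.** The raw range spans that figure; the baseline-adjusted range stays below it.
- **That compliance data are formally committed to setting the next trial's dose.** The text says only that they will help optimise it.

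The point is worth acting on because the correction is cheap.

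**What to change.** - **Significance, combined exercise and CT:** replace the dose-response objective with a descriptive analysis of compliance by arm and of its association with outcome, labelled as associational.
- **Data Management and Analysis:** adjust that association for baseline cognition and baseline peak VO2, in addition to the covariates already listed. State that effect sizes for the next trial come from the randomised contrasts, and that the compliance slope will not be used to choose its dose.
- **Exercise adherence:** score adherence against weeks prescribed, not weeks walked.
- **Adherence paragraph:** keep adherence out of the intent-to-treat model and report it alongside.
- **Optional complier-average effect:** if one is wanted, use randomised arm as the instrument and any CT uptake, or minutes, as the exposure, not the 80% cut-off. State its assumptions, including that assignment to CT affects outcome only through the training.

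The cost is wording plus one additional analysis of data already being collected. The dose claim is given up, and any complier estimate will have a wider interval than the randomised contrast.

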confounding variable of receiving attention from a healthcare professional. Instruction on stretching and flexibility movements is also expected to reduce attrition and patient dissatisfaction and to better ensure concealment of group allocation. These time-equivalent, flexibility/stretching movements have been previously piloted and will serve as the “placebo exercise condition.” In pilot evaluations they were well received, but were not strong enough to influence outcomes. The AC education placebo component will be delivered as soon as feasible after baseline (T1). The first 2 weeks of the intervention phase will include 2 home visits to demonstrate stretching and flexibility movements and to discuss educational materials. Weekly telephone calls will then be made for the next 10 weeks to discuss educational materials and to answer questions about stretching movements. An appointment will be made for participants to come to the ACTSI to collect T2 measures; this will occur at weeks 13 and 14. From weeks 15-24 bi-monthly telephone contact will be used to encourage continued adherence to the AC intervention. At the end of 24 weeks, a final visit to the ACTSI will be arranged and T3 measures will be taken. For ethical and cardiovascular health reasons, the AC group will be advised to exercise, but will not be provided with an exercise prescription or self-monitoring equipment since these have been shown to influence exercise adherence and exercise self-efficacy and may confound study outcomes.¹⁰⁴⁻¹⁰⁵

Groups 2 and 3 Exercise Prescription. Groups 2 & 3 will receive the same exercise prescription using a progressive moderate intensity aerobic protocol. To ensure that participants achieve adequate training stimulus, dose-specific exercise will be based on maximum heart rate (HR) obtained during symptom limited, modified Balke treadmill tests¹⁰⁶⁻¹⁰⁷ conducted by an exercise physiologist and supervising cardiologist in the

	Wk 1-2	Wk 3-4	Wk 5-7	Wk 8-9	Wk 10-12
Intensity	60%	60%	70%	70%	70%
Duration	30 mins	45 mins	45 mins	45 mins	45 mins
Frequency	3 x/wk	3 x/wk	3 x/wk	3 x/wk	3 x/wk

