CIN. Target heart rate (THR) using the 60% to 70% of maximum HR achieved on the cardiopulmonary exercise test (CPET) will be used to monitor the intensity and training response for aerobic exercise. Each participant will be provided with an individualized THR zone based on CPET results.¹⁰⁷ Under the supervision of a research nurse, participants will begin the walking sessions at 60% of THR and increase to 70% by week 5 as shown in Table 2. In our pilot with HF patients, a progressive moderate intensity level exercise program yielded positive outcomes with no adverse events, was appealing to participants and adherence rates were 80% or higher.

Group 2: EX/CT (UC + aerobic exercise + cognitive training) The first 2 weeks of the study will consist of 2 consecutive weekly home visits by the research nurse to demonstrate use of the HR monitor, pedometer and the CT program, Brain Fitness (Posit, San Francisco, CA detailed below). The research nurse will supervise one walking session during the first 2 weeks to ensure the safety of the participant and that he/she understands how to use the Polar HR monitor and pedometer and how to complete the walking logs. During the first 2 weeks, the research nurse will also provide training and demonstrate how to use the Brain Fitness computerized cognitive training program designed to be completed in 40 sessions over 12 weeks. We expect that participants will require additional time (at least 30 minutes each time) in the first 2 weeks to learn how to use and access the Brain Fitness program. The weekly schedules are provided in table 1.

The weekly schedules are provided in table 1.

Brain Fitness Computer Training: is based on the principles of positive brain plasticity and designed for use by adults. The training program (“Brain Fitness”) is focused on speech reception to strengthen an individual’s memory for speech. It has 6 modules names Hi-Lo, Tell Us Apart, Match It, Listen and Do, Sound Replay and Story Teller. Research to date has found: 1) participants with limited or no computer experience were capable of learning to perform the training exercises, 2) the training was safe and well tolerated by participants, and 3) healthy participants who trained on Brain Fitness showed on average a 1/3 standard deviation of improvement in memory, concentration and cognition, and 4) it has been tolerated well in patients in HF in a prior study.¹⁶

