Group 3: Ex only group (UC + aerobic exercise). The same exercise protocol will be used as above without the computer training.

Exercise adherence. To be 100% adherent for exercise sessions, participants in both groups 2 and 3 must document walking weekly at the prescribed intensity/duration on the exercise log. Participants will record on a calendar provided: maximum HR achieved; rate of perceived exertion (RPE) during walk; and number of steps walked during the walking sessions. Polar HR monitors and pedometers (described in instruments) will be used to objectively document exercise intensity (i.e., maximum HR and RPE achieved), duration, walking adherence and progression. The Polar HR monitor and pedometer data will be downloaded during each home visit during the first 2 weeks to track exercise duration and steps walked. At T2, data collected from the HR monitors and pedometers will also be downloaded to document exercise adherence. A total summary adherence score will be calculated by summing and dividing weekly adherence scores by total number of weeks walked.

CT adherence. The total number of minutes for the full Brain Fitness program is approximately 2400 minutes over 8 weeks. Patients will be considered adherent if they meet or exceed 80% of the required minutes for the intervention. Total number of minutes can be accessed from the program to monitor adherence.

VARIABLES, DEFINITIONS AND MEASURES. Variables, operational definitions and methods are described below and in Table 3. Questionnaires will be administered at the time of the visit by a trained research assistant blinded to group allocation. Core services and Center activities will greatly enhance the success of this study. Through training and monitoring in administration and scoring of the core test battery, regular consultation with the BMC to monitor implementation issues, systematic data management and analysis, and support in using these findings to prepare an RO1 application, this study will achieve its aims and further the goals of this Center.

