Exercise Adherence	Polar HR (intensity, duration and frequency), walk calendars, pedometer, nurse telephonic log	10 minutes	3 and 6 months
CT adherence	Brain Fitness program, nurse telephonic log	NA	

Physical Function will be assessed using the **modified Balke maximal treadmill test** ¹⁰⁶⁻¹⁰⁷ to determine peak oxygen consumption (peak VO_2), maximum HR for exercise prescription and to screen for cardiac contraindications to exercise according to the (AHA/ACC) guidelines. ¹⁰² **Physiological status.** The serum biomarker **BDNF** will be collected in the CIN by a research nurse or phlebotomist, the assays will be stored at -80 degrees until processed by the ACTSI biocore lab using the manufacturer's ELISA guidelines.

QOL. The **Kansas City Cardiomyopathy Questionnaire (KCCQ)** ¹¹⁰ is a reliable and well validated 23-item, disease specific questionnaire that quantifies physical function, symptoms, social function, and HRQOL in HF. ¹¹¹⁻¹¹²

Adherence. Step counts will be indirectly assessed using the Omron HJ-7201ITC pedometer to count daily steps. ¹¹³⁻¹¹⁷ The 15 point (6-20) **Borg Rate of Perceived Exertion (RPE) Scale** ¹¹⁸ will be used to measure participants' subjective perception of effort. **Target heart range (THR)** ¹⁰⁷ using the HR reserve method will be used to monitor the intensity and training response to walking. Polar Beat ® Watch (FT4) ¹¹⁹ will be used to monitor intensity and duration of walking. ¹²⁰⁻¹²¹ Actual adherence to intervention protocols and study attrition rates will be included in an intent-to-treat analysis (CT & Ex).

Acceptability. During post-baseline visits and phone contacts, participant's opinions about the intervention, e.g. perceived usefulness, ease of use, barriers to adherence, perceived improvements in health, cognition, mood, quality of life will be collected. The PI will use content analytic techniques to assess acceptability and to identify themes suggesting possible revisions or alterations in the interventions that might improve acceptability.

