The potential risks associated with the walking intervention are anticipated to be minimal. Any potential cardiovascular (CV) events that poses risk to the participant is anticipated to be detected during the modified Balke maximal treadmill test. In addition, the duration of walking will be limited to 30 minutes during the first 2 weeks and at an intensity level (60%) that is not likely to result in any adverse CV events; if necessary participants can rest as needed until the 30 minute duration of walking is completed. Participants will wear a Polar HR monitor so that HR and intensity level can be closely monitored. Participants will undergo 2 supervised walking sessions prior to walking at home unsupervised; the risk associated with the unsupervised session therefore, is anticipated to be minimal. Participants in the study will be provided with detailed instructions on self-monitoring HR, BP and symptoms associated before, during and after walking. Each participant will be provided with a target heart rate range to stay within during the study period. Participants will be instructed to wear the Polar HR monitor during each exercise session. The participants will take their HR, and BP (if machine available) and weight prior to and after each walking session and record it in their walking calendar. Participants will be instructed to call the research nurse if their BP or HR is outside their normal range. If participants are symptomatic, experience increased shortness of breath or have a greater than 2 pound weight gain over the previous 24 hours, they will be instructed not to exercise. The participants will be instructed to take their medications as usual prior to exercise and instructed on proper attire for exercising. Demonstrations and return demonstrations of the Polar HR monitor will ensure they know how to wear the monitor around the chest as well as trouble shoot when the monitor does not display a HR. They will be instructed that if their HR approaches within 5-10 beats of the target HR range to slow the walking pace down. They will also be instructed if they have an ICD, to keep their HR 15 beats below the firing range at all times (usually set at higher than 170 beats per minute, so it is unlikely to interfere with training stimulus). In addition, they will be instructed to monitor their RPE using the Borg 6 to 20 scale, and to keep their RPE at 12-13 during the initial weeks and to gradually progress with instructions to 15 as stipulated in the protocol. Participants in the intervention groups will be advised to carry a cell phone when they walk at home in the event of an emergency or sudden event. Specifically, participants will be instructed to slow their pace if their HR increases to near THR as previously noted or if they become short of breath. Participants who have ischemic heart disease and prescribed nitroglycerin (NTG) will be instructed to carry their NTG with them during each walking sessions. If chest pain occurs during exercise, the participants will be told to stop exercising and to take a NTG as directed by their cardiologist. The participant will also be instructed if the chest pain continues to sit down and to call a relative or friend and to take another NTG if the chest pain does not subside. If the chest pain continues and is not relieved by NTG within 10 minutes they will be instructed to call 911. If the participant becomes moderately to severely dyspneic where they cannot talk while walking they will be instructed to stop walking until the dyspnea subsides. If the dyspnea continues once they have stopped walking for several minutes they will be instructed to call a relative or friend; if not dissipated they will be

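### The exercise prescription sets the walking target as a percentage of maximum heart rate, against the heart rate reserve method stated elsewhere; separately, the risk text counts two supervised walks where the procedures provide one

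*Combined protocol and SAP*

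**What the plan says.** Three places in the combined protocol and SAP set the heart rate basis for walking.

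- Groups 2 and 3 Exercise Prescription (C. Approach): "Target heart rate (THR) using the 60% to 70% of maximum HR achieved on the cardiopulmonary exercise test (CPET". It continues: "participants will begin the walking sessions at 60% of THR and increase to 70% by week 5 as shown in Table 2". Table 2 gives 60% for weeks 1–4 and 70% for weeks 5–12, three sessions a week, without saying what the percentages are of.
- Adherence (Variables, Definitions and Measures): the target range "using the HR reserve method will be used to monitor the intensity and training response to walking".
- Rationale for sample characteristics (E. Human Subjects Research): "For both exercise testing and training we will use the heart rate reserve method which takes into account" the resting rate. The reason given is to lessen the influence of beta-blockers.

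Several rules depend on this target. Both exercise arms share it: "Groups 2 & 3 will receive the same exercise prescription using a progressive moderate intensity aerobic protocol". For full adherence, participants "must document walking weekly at the prescribed intensity/duration on the exercise log". The fallback to perceived exertion (RPE 12–15) begins "For patients who are unable to schedule exercise during this time frame or exercise up to the prescribed heart rate". The walking-risk text under Potential Risks describes the first two weeks as "at an intensity level (60%) that is not likely to result in any adverse CV events", and tells participants to slow down when heart rate comes within 5–10 beats of the target range.

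On supervision, Group 2: EX/CT provides one nurse-supervised walk in the first two weeks. Group 3 follows the same exercise protocol, and Sources of research material gives one for both exercise arms. The walking-risk text counts two before unsupervised walking and concludes from this that the remaining risk is minimal. Table 1 lists two home visits and a supervised walk without settling the number.

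**The concern.** A percentage of maximum heart rate and the same percentage of heart rate reserve are different targets, and the prescription section is where staff would look first for the rule. A nurse who applies it literally would set a lower target than the one the protocol justifies elsewhere, for some patients one that is already met at rest.

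The target also feeds other parts of the study. Intensity is part of the exercise adherence definition, and the study aims to learn about adherence and possible dose response for a later trial. Who moves to RPE guidance depends on which heart rate counts as prescribed. The slow-down instruction and the 60% in the risk text take their meaning from the same base. The literal wording of 60% of THR adds to the confusion, because THR has just been defined as a percentage itself.

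The supervised-walk count is a separate and smaller matter: the risk text relies on a safeguard that the procedures do not provide in full.

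**Working it through.** The plan states no heart rate figure to reproduce. The check compares the two formulas.

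**Inputs.** From Table 2: p = 0.60 in weeks 1–4 (4 × 3 = 12 sessions) and p = 0.70 in weeks 5–12 (8 × 3 = 24 sessions). Resting and peak rates are assumed: rest 60, 70 or 80 bpm; peak 100 to 150 bpm in steps of 10. It is also assumed that the Table 2 percentages apply under either method, since no others are given.

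**1. Difference between targets.**
- Percent of maximum: p × peak
- Reserve: rest + p × (peak − rest) = p × peak + (1 − p) × rest
- Reserve minus percent of maximum: (1 − p) × rest, whatever the peak

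| Assumed rest (bpm) | Gap at 60% | Gap at 70% |
|---|---|---|
| 60 | 0.4 × 60 = 24 | 0.3 × 60 = 18 |
| 70 | 0.4 × 70 = 28 | 0.3 × 70 = 21 |
| 80 | 0.4 × 80 = 32 | 0.3 × 80 = 24 |

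**2. Two worked patients.**
- Rest 70, peak 110. At 60%: 0.6 × 110 = 66 against 70 + 0.6 × 40 = 94. At 70%: 77 against 98.
- Rest 60, peak 150. At 60%: 90 against 114. At 70%: 105 against 123.

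For the first patient, the percent-of-maximum range of 66–77 bpm contains the resting rate of 70, so the slow-down rule could apply before walking starts. Under reserve the range is 94–98 bpm.

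**3. Targets at or below rest.** Of the 18 assumed rest/peak pairs, the percent-of-maximum target is no higher than rest in 7 at 60% (60/100, 70/100, 70/110, 80/100, 80/110, 80/120, 80/130) and in 3 at 70% (70/100, 80/100, 80/110). These counts show what is possible. They say nothing about how often it would occur in patients.

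**4. Could another reserve percentage reconcile the two?** The reserve percentage equivalent to 60% of maximum is (0.6 × peak − rest) / (peak − rest). At rest 60, peak 120 it is 12/60 = 20%; at rest 70, peak 120 it is 2/50 = 4%; at rest 60, peak 140 it is 24/80 = 30%. It varies by patient, so no single reserve percentage makes the two rules agree.

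**5. The literal 60% of THR.** If THR is already 60–70% of maximum, 60% of it is 36–42% of maximum (0.6 × 0.6 and 0.6 × 0.7), which cannot be intended.

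**6. Supervised walks.** Procedures: one. Risk text: two. Adding a walk at the second home visit would not by itself make the risk text true. The visits fall in consecutive weeks and Table 2 asks for three walks a week from week 1, which leaves 3 − 1 = 2 unsupervised walks in week 1.

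**The case against.** The strongest reply is that the protocol largely settles the method. The Rationale states reserve for both testing and training and explains why, and the Adherence paragraph agrees. The prescription's reliance on the treadmill maximum fits reserve too, because reserve needs a peak. That the percent-of-maximum rule can give targets at or below rest also suggests loose wording more than a second intended dosing rule. This stands. A reader might infer that the exercise dose has no defined basis at all; the documents do not support that.

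A reader might also take the bpm gap as a gap in exercise actually done. It is a gap between calculated targets. Participants are told to hold RPE at 12–13 at first and to progress to 15, symptomatic participants are not advanced until they manage 45 minutes at RPE 15 or below, and the stop rules apply whichever formula is used. The Exercise adherence paragraph records both heart rate and RPE and states no heart rate cut-off for scoring, so an effect on adherence scores arises only as far as intensity is judged against the heart rate target.

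Nor does the conflict show bias in ExCT versus Ex. The two arms share one prescription, so that comparison is unaffected if one method is used in both. The study is also exploratory.

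What remains is that the prescription sentence, as written, gives a rule that contradicts the stated method.

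**Conclusion.** The point holds as an internal contradiction with a clear outlier. The prescription sentence should give way to the reserve method stated in Adherence and in the Rationale. If the Table 2 percentages apply to both methods, following the sentence literally sets targets lower by 24–32 bpm in weeks 1–4 and 18–24 bpm in weeks 5–12, for assumed resting rates of 60–80 bpm. The direction and the formula do not depend on peak rate; the bpm values rest on assumed heart rates. The contradiction matters for the prescribed dose, for intensity adherence, for the switch to RPE and for the slow-down rule. It is worth correcting because the text is wrong as written and the correction is cheap.

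The supervised-walk discrepancy weakens one sentence of the risk statement. A reader might infer from it that participants lack adequate safety oversight. The documents do not support that: one supervised walk, heart rate monitoring, RPE limits and stop rules all remain.

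**What to change.** - **Confirm first.** The investigators and study cardiologist should confirm that 60–70% is the intended percentage of reserve and that it fits RPE 12–15.
- **Exercise prescription.** Replace the percent-of-maximum sentence and the 60% of THR wording with: target = rest + p × (peak − rest), using resting heart rate and the peak from the treadmill test.
- **Dependent text.** Label the percentages in Table 2 and in the walking-risk text as percent of heart rate reserve. Judge intensity adherence and apply the slow-down rule against that target.
- **Supervised walks.** Change two to one in the walking-risk text and restate the minimal-risk sentence on that basis. Keep two walks only if unsupervised walking is delayed until after the second home visit.

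The cost is protocol wording and revised staff and participant instructions; the formula needs nothing beyond resting rate and treadmill peak. The one downside is that any staff who had followed the percent-of-maximum sentence would have to raise targets, by 18–32 bpm under the assumptions above, and that needs a safety check before it is applied.
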